7.4.3 Dosage Adjustments, Delays, Rules for Withholding or Restarting, Permanent Discontinuation

7.4.3.1 Amgen Investigational Product: AMG 592

No dosage adjustments are allowed in either the phase 1b or phase 2 parts of the study. The reason for dose change of investigational product is to be recorded on each subject's CRF.

7.5 Preparation/Handling/Storage/Accountability

Guidance and information on preparation, handling, storage, accountability, destruction, or return of the investigational product during the study are provided in the IPIM.

7.6 Treatment Compliance

Subjects will receive the SC doses of AMG 592 at the research facility administered by qualified study personnel for the duration of the study.

7.7 Treatment of Overdose

The effects of overdose of AMG 592 are not known.

7.8 Prior and Concomitant Treatment

7.8.1 Prior Treatment

Prior therapies that were being taken/used from 6 months prior to the first dose of investigational product will be collected. Collect complete prior therapy history for RA. For prior therapies collect therapy name, indication, dose, unit, frequency, route, start date and stop date.

7.8.2 Concomitant Treatment

Throughout the study, investigators may prescribe any concomitant therapies or treatments deemed necessary to provide adequate supportive care except for those listed in [Section 7.1.7](#) and those mentioned below.

Concomitant therapies are to be collected from first dose of investigational product through the safety follow-up. Collect therapy name, indication, dose, unit, frequency, route, start date and stop date

7.8.2.1 Methotrexate

All subjects must maintain a stable dose and the same route of administration (ie, oral or subcutaneous) of methotrexate through the treatment period in both the phase 1b and phase 2a parts of the study. The doses of methotrexate should be taken on the same day of the week (± 2 days). After the treatment period the dose of methotrexate may be adjusted.

Approved

Subjects must also take folic acid or folinic acid supplementation during the study. The dose of folic acid or folinic acid will be as per investigator judgment or according to local standard of care. The dose of folic acid may be adjusted in response to methotrexate-related toxicity.

7.8.2.2 Analgesics and NSAIDs

If the study subject enters the study taking a stable dose of acetaminophen, analgesics, or NSAIDs on a scheduled basis (see [exclusion criterion 221](#)), the dose can be reduced or discontinued during the study if necessary for safety reasons or standard of care. No new analgesics or NSAIDs may be added during the treatment period.

During treatment period analgesics or NSAIDs must not be used within 12 hours before a scheduled study visit where efficacy is assessed, with the exception of oxycontin which may not be used within 24 hours of a scheduled study visit where efficacy is assessed. In both the phase 1b and phase 2a parts of the study, efficacy is assessed at baseline and at weeks 4, 8, and 12.

[figure not shown]
After the treatment period, analgesics and NSAIDs may be added as required or the dose adjusted per investigator judgment in both the phase 1b and phase 2a parts of the study.

7.8.2.3 Corticosteroids

Subjects entering the study while taking oral corticosteroids cannot change their dose during the treatment period. Addition of new corticosteroids regardless of route of administration is not allowed. After the treatment period new corticosteroids, administered by any route may be added or dose adjusted per investigator judgment. Investigators should make every effort to reduce the steroid dose for subjects responding to investigational product and to taper steroids after the resolution of disease flare.

7.8.2.4 DMARDS

In the phase 1b part of the study only, subjects entering the study taking sulfasalazine, hydroxychloroquine, minocycline or leflunomide cannot change their dose during the initial treatment period. After the treatment period, new non-biologic DMARDs may be added or dose adjusted per investigator judgment.

Approved

8. Discontinuation Criteria

Subjects have the right to withdraw from investigational product and/or other protocol-required therapies, protocol procedures, or the study as a whole at any time and for any reason without prejudice to their future medical care by the physician or at the institution.

The investigator and/or sponsor can decide to withdraw a subject(s) from investigational product, device, and/or other protocol-required therapies, protocol procedures, or the study as a whole at any time prior to study completion for the reasons listed in [Sections 8.1, 8.2.1, and 8.2.2](#).

8.1 Discontinuation of Study Treatment

Subjects can decline to continue receiving investigational product and/or other protocol-required therapies or procedures at any time during the study but continue participation in the study. If this occurs, the investigator is to discuss with the subject the appropriate processes for discontinuation from investigational product or other protocol-required therapies and must discuss with the subject the possibilities for continuation of the Schedule of Activities (see [Table 2-1](#), [Table 2-2](#) and [Table 2-3](#)) including different options of follow-up (eg, in person, by phone/mail, through family/friends, in correspondence/communication with other treating physicians, from the review of medical records) and collection of data, including endpoints, adverse events, disease-related events and must document this decision in the subject's medical records. Subjects who have discontinued investigational product and/or other protocol-required therapies or procedures should not be automatically removed from the study. Whenever safe and feasible, it is imperative that subjects remain on-study to ensure safety surveillance and/or collection of outcome data.

Subjects may be eligible for continued treatment with Amgen investigational product(s) and/or other protocol-required therapies by a separate protocol or as provided for by the local country's regulatory mechanism, based on parameters consistent with [Appendix 3](#).

Reasons for removal from protocol-required investigational product(s) or procedural assessments include any of the following:

- Decision by Sponsor
- Lost to follow-up
- Death
- Ineligibility determined

- Protocol deviation
- Non-compliance
- Adverse event
- Subject request
- Requirement for alternative therapy
- Protocol-specified criteria; see [Section 7.4.2](#)
- Pregnancy

8.2 Discontinuation From the Study

Withdrawal of consent for a study means that the subject does not wish to receive further protocol-required therapies or procedures, and the subject does not wish to or is unable to continue further study participation. Subject data up to withdrawal of consent will be included in the analysis of the study, and where permitted, **publicly** available data can be included after withdrawal of consent. The investigator is to discuss with the subject appropriate procedures for withdrawal from the study, and must document the subject's decision to withdraw in the subject's medical records.

If a subject withdraws from the study, he/she may request destruction of any samples taken and not tested, and the investigator must notify Amgen accordingly (see [Appendix 6](#) for further details). Refer to the Schedule of Activities for data to be collected at the time of study discontinuation and follow-up and for any further evaluations that need to be completed.

8.2.1 Reasons for Removal From Washout, Run-in or Invasive Procedures

Not applicable to this study

8.2.2 Reasons for Removal From Study

Reasons for removal of a subject from the study are:

- Decision by sponsor
- Withdrawal of consent from study
- Death
- Lost to follow-up

8.3 Lost to Follow-up

A subject will be considered lost to follow-up if he or she repeatedly fails to return for scheduled visits and is unable to be contacted by the study site.

Approved

The following actions must be taken if a subject fails to return to the clinic for a required study visit:

- The site must attempt to contact the subject and reschedule the missed visit as soon as possible and counsel the subject on the importance of maintaining the assigned visit schedule and ascertain whether or not the subject wishes to and/or is able to continue in the study.
- In cases in which the subject is deemed lost to follow-up, the investigator or designee must make every effort to regain contact with the subject (where possible, 3 telephone calls and, if necessary, a certified letter to the subject's last known mailing address or local equivalent methods). These contact attempts are to be documented in the subject's medical record.
- If the subject continues to be unreachable, he/she will be considered to have withdrawn from the study with a primary reason of lost to follow-up.
- For subjects who are lost to follow-up, the investigator can search **publicly** available records (where permitted) to ascertain survival status. This ensures that the data set(s) produced as an outcome of the study is/are as comprehensive as possible.

9. Study Assessments and Procedures

Study procedures and their time points are summarized in the Schedule of Activities (see [Table 2-1](#), [Table 2-2](#), and [Table 2-3](#)).

As protocol waivers or exemptions are not allowed if an enrolled subject is subsequently determined to be ineligible for the study, this must be discussed with the sponsor immediately upon occurrence or awareness to determine if the subject is to continue or discontinue study treatment.

Adherence to the study design requirements, including those specified in the Schedule of Activities, is essential and required for study conduct.

9.1 General Study Periods

9.1.1 Screening, Enrollment and Randomization

Informed consent must be obtained before completing any screening procedure or discontinuation of standard therapy for any disallowed therapy. After the subject has signed the informed consent form, the site will register the subject in the IVRS and screen the subject in order to assess eligibility for participation. The screening window is up to 28 days.

All screening evaluations must be completed and reviewed to confirm that potential subjects meet all eligibility criteria. The investigator will maintain a screening log to record details of all subjects screened and to confirm eligibility or record reasons for screening failure, as applicable.

If a subject has not met all eligibility criteria at the end of the screening period, the subject will be registered as a screen fail. Screen fail subjects may be eligible for rescreening 2 times.

[figure not shown]
Rescreen subjects must first be registered as screen failures in IVRS and subsequently registered as rescreens. Once the subject is registered as rescreened, a new 28 day screening window will begin. Subjects will retain the same subject identification number assigned at the original screening. Subjects rescreening within the original 28-day screening period only need to repeat the assessment(s) that did not originally meet the eligibility criteria; all other initial screening assessments do not need to be repeated. Subjects rescreening after the original 28-day screening period has ended must repeat all screening procedures including being re-consented. However, a tuberculosis test that was negative at the original screening does not need to be repeated as long as the subject has not had exposure to active tuberculosis after the original screening tuberculosis test was completed.

9.1.2 Treatment Period

Visits will occur per the Schedule of Activities ([Table 2-1](#) and [Table 2-3](#)). On-study visits may be completed within a visit window of ± 1 day for phase 1b and ± 2 days for phase 2a from the scheduled dose date. The date of the first dose of investigational product is defined as day 1. All subsequent doses and study visits will be scheduled based on the day 1 date. Investigational product should be administered after all other study procedures have been completed, except at day 1 and week 12 in the phase 1b part of the study per the Schedule of Activities ([Table 2-1](#)).

9.1.3 Follow-up/Safety Follow-up/End of Study for Phase 1b

After the 12-week treatment period, subjects in the phase 1b part of the study will be followed for an additional 6 weeks up until week 18 for collection of additional safety, PK and PD data as described in the Schedule of Activities ([Table 2-2](#)). For subjects who complete the study at week 18, the visit includes all required safety follow-up data collection. All subjects who terminate the study early (ie, prior to completing the week 18 visit), will complete an Early Termination visit consisting of all assessments included in the week 12 day 85 pre-dose visit. In addition, a safety follow-up visit will occur 6 weeks (± 3 days) after the last dose of investigational product to collect all required safety data including adverse events, serious adverse events, disease related events, concomitant therapies, safety labs/assessments, anti-AMG 592 antibody, and urine pregnancy test.

9.2 Description of General Study Assessments and Procedures

The sections below provide a description of the individual study procedures for required timepoints.

9.2.1 General Assessments

9.2.1.1 Informed Consent

All subjects must sign and personally date the IRB/IEC approved informed consent before any study-specific procedures are performed.

9.2.1.2 Demographics

Demographic data collection including sex, age, race, and ethnicity will be collected in order to study their possible association with subject safety and treatment effectiveness. Additionally demographic data will be used to study the impact on biomarkers variability and pharmacokinetics of the protocol-required therapies.

9.2.1.3 Medical History

The Investigator or designee will collect a relevant medical and surgical history that started within 5 years or as necessary for chronic or co-morbid conditions prior to enrollment through the start of the adverse event reporting period. Medical history will include information on the subject's concurrent medical conditions. Record all findings on the medical history CRF. In addition to the medical history above, RA history must date back to the original diagnosis. The current toxicity grade will be collected for each condition that has not resolved.

9.2.1.4 Physical Examination

Physical examination will be performed as per standard of care. Physical examination findings should be recorded on the appropriate CRF (eg, medical history, event).

9.2.1.5 Physical Measurements

[figure not shown]
Weight in kilograms and height in centimeters should be measured without shoes.

Approved

9.2.1.6 Substance Use History

For the phase 1b part of the study, obtain a detailed history of prior and/or concurrent use of alcohol and of nicotine or tobacco containing products.

[figure not shown]
9.2.2 Efficacy Assessments

[figure not shown]
[figure not shown]

Approved

9.2.2.2 DAS28-CRP

The DAS28-CRP will be calculated in the phase 1b part of the study to determine subject eligibility during screening.

Approved

9.2.3 Safety Assessments

Planned timepoints for all safety assessments are listed in the Schedule of Activities.

9.2.3.1 Adverse Events

9.2.3.1.1 Time Period and Frequency for Collecting and Reporting Safety Event Information

9.2.3.1.1.1 Disease-related Events

Disease-related events are defined in [Appendix 4](#).

The investigator is responsible for ensuring that all disease-related events observed by the investigator or reported by the subject that occur after the first dose of investigational product(s) through the safety follow-up are reported using the Event CRF.

Disease-related events assessed by the investigator to be more severe than expected and/or related to the investigational product(s)/study treatment/protocol-required therapies, and determined to be serious, must be reported on the Event CRF as serious adverse events.

Disease-related events pre-defined for this study include joint pain, joint stiffness, joint swelling, worsening of rheumatoid arthritis.

9.2.3.1.1.2 Adverse Events

The adverse event grading scale to be used for this study will be the Common Terminology Criteria for Adverse Events (CTCAE) and is described in [Appendix 4](#).

The investigator is responsible for ensuring that all adverse events observed by the investigator or reported by the subject that occur after first dose of investigational product through the safety follow-up are reported using the Event CRF.

9.2.3.1.1.3 Serious Adverse Events

The investigator is responsible for ensuring that all serious adverse events observed by the investigator or reported by the subject that occur after signing of the informed consent through the safety follow-up are reported using the Event CRF.

All serious adverse events will be collected, recorded and reported to the sponsor or designee within 24 hours, as indicated in [Appendix 4](#). The investigator will submit any updated serious adverse event data to the sponsor within 24 hours of it being available.

The criteria for grade 4 in the CTCAE grading scale differs from the regulatory criteria for serious adverse events. It is left to the investigator's judgment to report these grade 4 abnormalities as serious adverse events.

9.2.3.1.1.4 Serious Adverse Events After the Protocol-required Reporting Period

There is no requirement to monitor study subjects for serious adverse events following the protocol-required reporting period or after end of study. However, these serious adverse events can be reported to Amgen. Per local requirements in some countries, investigators are required to report serious adverse events that they become aware of after end of study. If serious adverse events are reported, the investigator is to report them to Amgen within 24 hours following the investigator's knowledge of the event.

Serious adverse events reported outside of the protocol-required reporting period will be captured within the safety database as clinical trial cases and handled accordingly based on relationship to investigational product.

The method of recording, evaluating, and assessing causality of adverse events, disease-related events, and serious adverse events and the procedures for completing and transmitting serious adverse event reports are provided in [Appendix 4](#).

Approved

9.2.3.1.1.5 Serious Adverse Events That Are Not to be Reported by the Sponsor to Regulatory Agencies in an Expedited Manner

Not applicable

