7.4.2.2 Dose Cohort Stopping Rules

The following dose cohort stopping rules will be used in the phase 1b part of the study. Dosing will be stopped or modified as shown in [Table 7-1](#).

Approved

Table 7-1. Dose Cohort Stopping Rules

| Scenario | Action |
|--|--|
| 
Occurrence of a CTCAE version 4.03 Grade 3 adverse event deemed related to investigational product in 2 or more subjects within in a single dosing cohort
 | 
Stop dosing and convene DLRM (if event occurs outside the regularly scheduled DLRM)
 
Review adverse event and all relevant safety data for evidence of relationship to treatment and clinical or medical significance
 
Consider unblinding, as appropriate^a
 
Upon majority vote by the DLRM members, one of the following recommendations may be made
 
 • stop enrollment of the cohort (if applicable) • enrollment of the cohort may resume as planned • the cohort may be expanded at the same dose • enrollment of the study may continue at a lower dose 
OR
 
Upon unanimous vote by the DLRM members, 1 of the following recommendations may be made:
 
 • escalation to an intermediate dose (a dose lower than the next planned dose) may take place • escalation to the next planned dose may occur |
| 
Any occurrence of a CTCAE version 4.03 ≥ Grade 4 adverse event
 | 
Stop dosing additional subjects in the cohort and convene DLRM (if the event occurs outside the regularly scheduled DLRM)
 
Review adverse event and all relevant safety data for evidence of relationship to treatment and clinical or medical significance.
 
Consider unblinding to determine relatedness to investigational product^a
 
If the adverse event is determined by majority vote of the DLRM members to be related to the investigational product and clinically or medically significant, no further doses should be administered at this dose and no dose escalation should proceed. Enrollment of the study may continue at a lower dose or a lower dose cohort may be added to the study.
 
Otherwise, upon majority vote of the DLRM members, one of the following recommendations may be made:
 
 • enrollment of the cohort may resume as planned • the cohort may be expanded at the same dose • enrollment of the study may continue at a lower dose or a lower dose cohort may be added to the study |

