The investigator must permit study-related monitoring, audits, [IRB/IEC] review, and regulatory agency inspections and provide direct access to source data documents.

The sponsor or designee is responsible for the data management of this study including quality checking of the data.

Clinical monitors will perform ongoing source data verification to confirm that data entered into the CRF by authorized site personnel are accurate, complete, and verifiable from source documents; that the safety and rights of subjects are being protected; and that the study is being conducted in accordance with the currently approved protocol and any other study agreements, ICH GCP, and all applicable regulatory requirements per the sponsor's monitoring plan.

The investigator agrees to cooperate with the clinical monitor to ensure that any problems detected in the course of these monitoring visits, including delays in completing CRFs, are resolved.

The Amgen representative(s) and regulatory authority inspectors are responsible for contacting and visiting the investigator for the purpose of inspecting the facilities and, upon request, inspecting the various records of the clinical study (eg, CRFs and other pertinent data) provided that subject confidentiality is respected.

In accordance with ICH GCP and the sponsor's audit plans, this study may be selected for audit by representatives from Amgen's Quality, Compliance, and Audit function (or designees). Inspection of site facilities (eg, pharmacy, protocol-required therapy storage areas, laboratories) and review of study-related records will occur to evaluate the study conduct and compliance with the protocol, ICH GCP, and applicable regulatory requirements.

Retention of study documents will be governed by the Clinical Trial Agreement.

Amgen (or designee) will perform Self-Evident Corrections (SEC) to obvious data errors in the clinical trial database. SECs will be documented in the CRF Standard Instructions and the CRF Specific Instructions, both of these will be available through the EDC system. Examples of obvious data errors that may be corrected by Amgen (or designee) include deletion of obvious duplicate data (ie, the same results sent twice with the same date with different visit, [eg, week 4 and early termination]) and updating a specific response if the confirming datum is provided in the "other, specify" field (eg, for race, reason for ending study).

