| 
• When an adverse event, disease-related event or serious adverse event occurs, it is the responsibility of the investigator to review all documentation (eg, hospital progress notes, laboratory, and diagnostics reports) related to the event.• The investigator will then record all relevant adverse event/disease-related event/serious adverse event information in the Event case report form (CRF).
○ Additionally, the investigator is required to report a fatal disease-related event on the Event CRF.• The investigator must assign the following adverse event attributes:
○ Adverse event diagnosis or syndrome(s), if known (if not known, signs or symptoms);○ Dates of onset and resolution (if resolved);○ Severity (or toxicity defined below);○ Assessment of relatedness to investigational product, other protocol-required therapies; and○ Action taken.• If the severity of an adverse event changes from the date of onset to the date of resolution, record as a single event with the worst severity on the Event CRF.• It is not acceptable for the investigator to send photocopies of the subject's medical records to the sponsor in lieu of completion of the Event CRF page. |

Approved

Adverse Event, Disease-related Event (if applicable) and Serious Adverse Event Recording

- If specifically requested, the investigator may need to provide additional follow-up information, such as discharge summaries, medical records, or extracts from the medical records. In this case, all subject identifiers, with the exception of the subject number, will be blinded on the copies of the medical records before submission to Amgen.
- The investigator will attempt to establish a diagnosis of the event based on signs, symptoms, and/or other clinical information. In such cases, the diagnosis (not the individual signs/symptoms) will be documented as the adverse event/serious adverse event.

Evaluating Adverse Events and Serious Adverse Events

Assessment of Severity

The investigator will make an assessment of severity for each adverse event and serious adverse event reported during the study. The assessment of severity will be based on:

The **Common Terminology Criteria for Adverse Events (CTCAE)**, version 4.0 which is available at the following location:
http://ctep.cancer.gov/protocolDevelopment/electronic_applications/ctc.htm

Assessment of Causality

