- New or updated information will be recorded in the originally completed Event CRF.
- The investigator will submit any updated serious adverse event data to Amgen within 24 hours of receipt of the information.

Reporting of Serious Adverse Event

Serious Adverse Event Reporting via Electronic Data Collection Tool

- The primary mechanism for reporting serious adverse event will be the electronic data capture (EDC) system via the Safety Report Form.
- If the EDC system is unavailable for more than 24 hours, then the site will report the information to Amgen using an electronic Serious Adverse Event (eSAE) Contingency Report Form (see [Figure 12-1](#)) within 24 hours of the investigator's knowledge of the event.
- The site will enter the serious adverse event data into the electronic system as soon as it becomes available.
- After the study is completed at a given site, the EDC system will be taken off-line to prevent the entry of new data or changes to existing data.
 - If a site receives a report of a new serious adverse event from a study subject or receives updated data on a previously reported serious adverse event after the EDC has been taken off-line, then the site can report this information on a paper Serious Adverse Event Report Form (see [Figure 12-1](#)).

Adverse Device Effects: Recording, Evaluating and Reporting

- Any adverse event resulting from an adverse device effect that occur during the study will be documented in the subject's medical records, in accordance with the investigator's normal clinical practice, and on the Event CRF page.
- It is very important that the investigator provides his/her assessment of causality (relationship to the medical device provided by Amgen at the time of the initial report and describes any corrective or remedial actions taken to prevent recurrence of the incident.

Figure 12-1. Sample Electronic Serious Adverse Event Contingency Form

| | | | | | | | | | | | | | | |
|--|----------|--|--|--|--------------------------------------|--|--|--|--|---|-----------|---|--|---|
| AMGEN Study # 20170149 AMG 592 | | Electronic Serious Adverse Event Contingency Report Form For Restricted Use | | | | | | | | | | | | |

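### The Grade 3 cohort stopping rule counts non-serious events, but the protocol sets no deadline for telling the sponsor about them, so a stop can come late when the affected subjects are at different sites

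*Protocol*

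**What the plan says.** The Grade 3 row of Table 7-1 (protocol 7.4.2.2) is triggered by a "Grade 3 adverse event deemed related to investigational product in 2 or more subjects within in a single dosing cohort". Seriousness is not a condition. The action is to stop dosing and convene a DLRM, off schedule if need be. Footnote a adds that dosing will not be stopped by decision unless the treatment assignment has been unblinded.

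Reporting is organised differently. Section 9.2.3.1.1.3 states: "All serious adverse events will be collected, recorded and reported to the sponsor or designee within 24 hours". For adverse events in general, 9.2.3.1.1.2 says only that those "that occur after first dose of investigational product through the safety follow-up are reported using the Event CRF". Appendix 4 repeats that events are recorded on that form and gives no time limit. Its outage provision, "If the EDC system is unavailable for more than 24 hours, then the site will report the information to Amgen", belongs to the part on serious adverse event reporting and uses a serious adverse event form.

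For Grade 4, 9.2.3.1.1.3 leaves it to the investigator's "judgment to report these grade 4 abnormalities as serious adverse events".

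**The concern.** The stopping rule is a main protection for subjects during dose escalation. Its Grade 3 limb depends on grade, relatedness and a count within a cohort, while the stated fast route to the sponsor depends on seriousness. A non-serious related Grade 3 event counts toward the stop but has no deadline for reaching the sponsor.

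This matters most when the two affected subjects are at different sites. Each site then knows of one event and has no trigger. Only someone who holds both reports can see that the count is met. If one report is slow, the unblinding, the DLRM and the stop all start late, and other subjects in the cohort can be dosed in the meantime.

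**Working it through.** **1. The time limits, set side by side.**

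| Item | Limit | Covers a non-serious related Grade 3 event? |
|---|---|---|
| Serious adverse events and their updates (9.2.3.1.1.3, 9.2.3.1.1.4, 9.2.3.1.3, Appendix 4) | 24 hours | No |
| Combined transaminase with bilirubin and/or INR elevation (Appendix 7) | 24 hours, because reported as serious | No, treated as serious |
| Pregnancy and lactation (9.2.3.1.5, Appendix 5) | 24 hours | No |
| Emergency unblinding by a site (7.3.1) | 24 hours | No |
| Other adverse events (9.2.3.1.1.2, Appendix 4) | None stated | Yes, Event CRF only |

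The SAP adds no limit.

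**2. What the missing limit does to the count.** Let t1 ≤ t2 be the times at which the two sites become aware of their qualifying events, and L1, L2 the lags until the sponsor has each report. The count is met at t2. The sponsor can see it at max(t1 + L1, t2 + L2). The delay is therefore

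D = max(t1 + L1, t2 + L2) − t2.

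- Both events serious: L1 and L2 are each at most 24 hours. Since t1 ≤ t2, D is at most 24 hours.
- Either event non-serious: that lag has no stated ceiling, so D has none.
- Both subjects at one site: the site knows at t2 and can alert the sponsor itself.

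**3. Scheduled meetings do not fill the gap.** The DLRM follows the week 4 visits (5.1.1, 7.4.2.1). Week 4 is day 29 and the week 12 dose is day 85, so for the last subject reviewed (85 − 29)/7 = 8 weeks of the dosing period remain. Table 7-1 itself provides for events between meetings.

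**4. The safeguards.**
- The unblinded early development lead monitors continuously (7.3.2), and the SAP refers to ongoing data review (9.1). Neither provision sets a time by which a site must enter an event.
- Central laboratory results (9.2.4) can show a laboratory grade, but not the investigator's view of relatedness, which the trigger needs.
- Unqueried data may be used at a DLRM (Appendix 3). That helps once a meeting is called.
- Sites must cooperate so that "any problems detected in the course of these monitoring visits, including delays in completing CRFs, are resolved". This anticipates late entry without limiting it.
- Investigators are told of related serious adverse event reports sent to authorities (9.2.3.1.4). That does not tell one site of another's non-serious event.

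**5. Grade 4.** A non-serious Grade 4 event also falls outside the 24-hour rule. The gap is smaller, because one event is enough and the site can recognise the trigger.

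**6. Scale.** The plan has no figure on notification. The probabilities in 10.1.1 reproduce (for example 1 − 0.75^6 = 82.2% and 1 − 0.80^12 = 93.1%) but concern at least one event of any kind. As an illustration only, take related Grade 3 rates of 5%, 10% and 20%, which are assumed. The chance of two or more affected AMG 592 subjects is 1 − (1 − p)^n − np(1 − p)^(n − 1):
- n = 6: 3.3%, 11.4%, 34.5%.
- n = 12: 11.8%, 34.1%, 72.5%.

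These count serious and non-serious events together. They show how often the rule might fire, not how often it would fire late.

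**The case against.** The strongest reply is that a deadline may exist elsewhere. The Amendment 1 rationale says the protocol was aligned with a DLRM SOP, and the documents also refer to CRF instructions, a data management plan, a monitoring plan and a separate SAP for the DLRM. None was supplied, and any of them could set an entry deadline. This stands. It limits the finding to the supplied text and may reduce the remedy to a cross-reference.

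A reader might go further and infer that the count runs over about 18 sites, so that usually only the sponsor can make it. The documents do not support that. Eighteen is the phase 1b total (5.2.2); a cohort of 8 can span at most 8 sites and one of 16 at most 16, and the actual spread is not stated. Section 3.2.5 points to possible clustering: most of the reports of worsening arthritis judged related came from one site. Grades are not given there, so it shows neither Grade 3 clustering nor a missed stop.

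It is also fair to say that the count alone does not settle the stop, because footnote a requires unblinding. That adds a step after the count; it does not make late notice harmless.

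Finally, the existing controls are real: dosing by site staff with a physician available, a central laboratory, continuous sponsor monitoring and 24-hour reporting of combined liver elevations. They reduce the chance of a long delay but set no limit on it.

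**Conclusion.** The concern holds on the supplied text, in limited form. The Grade 3 stopping trigger includes non-serious events, and no stated deadline brings those events to the sponsor. When the affected subjects are at different sites, neither site can see that the count is met, so unblinding, the DLRM and the stop can be late while others in the cohort are dosed.

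The size of the delay cannot be given. The CRF entry lag is not stated, the dosing interval is redacted, and the spread of cohorts over sites is unknown. A reader might take cohort size less two (8 − 2 = 6, or 16 − 2 = 14) as the number of subjects harmed or exposed. It is only a ceiling at planned sizes: enrolment is staggered, subjects finish or stop, and Amendment 3 reports many early dropouts in cohorts 2 and 3. Nor do the documents show that any stop in this trial was late.

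The conclusion rests on two assumptions: that no unsupplied document sets a deadline, and that the two subjects are not at the same site. Sample size, error rates and planned analyses are unaffected.

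**What to change.** In 9.2.3.1.1.2 and Appendix 4, with a cross-reference from Table 7-1, state that in phase 1b every related Grade 3 adverse event and every Grade 4 or higher adverse event, serious or not, is notified to the sponsor within 24 hours of site awareness. Extend the Appendix 4 contingency route to these events when the EDC system is down, and have the sponsor keep a running tally by cohort. In the notation above, D is then at most 24 hours from the second site's awareness.

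If an operational document already sets such a deadline, cite it in Table 7-1 instead.

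The cost is a short addition to the protocol and site instructions, the tally, and a few extra notifications in about 48 subjects. No visits or subjects are added, and the thresholds and actions in Table 7-1 stay as they are.
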